### III. Preliminary Studies/Progress Report:

(1) **CGM Therapy in Pregnancy with or without Remote Monitoring:** The Barbara Davis Center (BDC) for Diabetes has experience with research during pregnancy. BDC's clinical staff has cared for hundreds of pregnant women with diabetes (mostly with T1D), 60-70 per year. The principal investigator (PI) of the proposed study directs the Pregnancy and Women's Health Clinic. The PI completed an open-label, investigator-initiated, study in pregnant women with T1D prospectively (n=40) stratified to (1) CGM Alone [women with Apple devices], or (2) CGM Share (DexCom, San Diego, CA) [women with an iPhone and followers with data-viewing devices], and retrospectively (n=8) to (3) no CGM. There were 48 women enrolled in the study (15 during preconception, 25 during the 1st trimester, 8 on retrospective chart review). All pregnant women were trained and started on a Dexcom G4 system. Women prospectively enrolled were given sensors throughout pregnancy for the G4 (provided by the study) or G5 system (provided by patient's health insurance). In the preconception group, 53% (8/15) became pregnant during the study period. Final analyses include 13 women in the CGM Alone group, 15 in CGM Share, and 8 in no CGM. SAPT was used in 86% (24/28) of the prospective and 75% (6/8) of the retrospective pregnancies. There were 3 episodes of SH (severe hypoglycemia, which is hypoglycemia requiring the assistance of a 3rd party) in 2 women. Interim data were presented at the ADA Scientific Sessions in 2016 and 2017, complete data were presented at ATTD in 2018. A1C over time, time spent >180 mg/dL, hypoglycemia fear scores, and neonatal hypoxemia were significantly lower in CGM Share users. The BDC can recruit and retain pregnant women with T1D into studies, and train them on SAPT devices.

(2) **CL in non-Pregnant Adults:** The BDC has extensive experience studying insulin pump technology. The BDC was 1 of the 10 sites involved in the pivotal study on the Medtronic 670G HCL system, which has been assessed in hotel and free-living conditions. The HCL system was studied in adolescents (n=30) and adults (n=94) with T1D for 3 months in free-living conditions. Adults were in the HCL mode a median of 88% of the time, A1C decreased from a mean of 7.3% to 6.8% (p<0.001), TIR (70-180 mg/dL) increased from 68.8% to 73.8% (p<0.001), and hypoglycemia (≤70 mg/dL) decreased from 6.4 to 3.4% (p<0.001) from run-in to study end. For adults, fasting TIR significantly increased (70 ± 21.2% run-in to 84.4 ± 12.1% study end, p<0.001). There were no episodes of SH or DKA. The sensor accuracy, measured as mean amplitude of relative

difference (MARD)  $\pm$  standard deviation between the sensor glucose (SG) and i-STAT venous glucose values, was 10%  $\pm$  8.7% in adults (10.3% for SG >180 mg/dL and 12.2% for SG  $\leq$ 70 mg/dL). The BDC can train subjects on the HCL system, follow glucose outcomes and device deficiencies, and retain subjects.

#### **IV. Research Methods**

##### **A. Outcome Measure(s):**

###### **Primary Outcomes:**

- 1) Safety of HCL therapy compared to SAPT in women with T1D throughout gestation and the early post-partum period assessed through episodes of severe hypoglycemia and time spent with glucose <54 mg/dL.
- 2) Indices of glucose control and fear of hypoglycemia in pregnant women with T1D using HCL or SAPT therapy throughout pregnancy and early post-partum. Indices of glucose control are time spent in the glucose target ranges <54 mg/dL and <63 mg/dL (hypoglycemia), 63-140 mg/dL (time in range), and >140 mg/dL and >180 mg/dL (hyperglycemia). Fear of hypoglycemia is assessed as behavior, worry, and total scores of fear of hypoglycemia determined by the Hypoglycemia Fear Survey.

###### **Secondary Outcomes:**

- 3) Safety of HCL therapy compared to SAPT in women with T1D throughout gestation and the early post-partum period assessed through episodes of diabetic ketoacidosis and skin reactions.
- 4) Indices of glucose control and fear of hypoglycemia in pregnant women with T1D using HCL or SAPT therapy throughout pregnancy and early post-partum. Secondary outcomes of indices of glucose control are mean glucose  $\pm$  standard deviation, J index, High Blood Glucose Index (HBGI), Low Blood Glucose Index (LBGI), duration of hypoglycemic episodes, Mean Amplitude of Glycemic Excursions (MAGE), and Continuous Overall Net Glycemic Action (CONGAn).
- 5) Quality of life and device acceptability in women with T1D throughout gestation and the early post-partum period as measured by scores from the MOS Short-Form 36 (quality of life) and Insulin Delivery Satisfaction Survey, Glucose Monitoring Satisfaction Survey, and INSPIRE (HCL only) questionnaires (device acceptability).
- 6) Maternal and fetal outcomes in pregnant women with T1D using HCL therapy compared to those using SAPT throughout gestation and in the early post-partum period. Maternal outcomes include preeclampsia/eclampsia, cesarean delivery, and gestational weight gain. Fetal outcomes include fetal loss (miscarriage or stillbirth), large-for-gestational age, and neonatal hypoglycemia.

##### **B. Description of Population to be Enrolled:**

We anticipate recruiting women with T1D for at least a year who are pregnant (11 weeks gestation or earlier) between the ages of 18 and 45 years old. We expect to screen up to 37 individuals, randomize up to 24 women, and have 20 completers (10 women per group).

##### **C. Study Design and Research Methods**

Overview: This is a two-center, prospective, 'open-label', single-blind, investigator-initiated randomized controlled pilot study evaluating HCL insulin delivery among pregnant women with T1D compared with SAPT throughout the 2nd and 3rd trimesters of gestation and the first 6 weeks of the post-partum period at the BDC and Ohio State University. Each institution will obtain IRB approval separately. The statistician will be blinded to treatment assignment, but the participants and clinical research team will not.

[figure not shown]
Study Design: Up to 37 women will be screened in the 1st trimester of pregnancy ( $\leq 11$  weeks gestation) over 10 months. All subjects meeting the initial inclusion/exclusion criteria will be invited to sign informed consent and participate in the study. The consent form must be signed by all women who wish to participate in the study, however there are two optional consent procedures: (1) providing specimens (blood and urine) to be stored in a biorepository for future research studies and (2) providing permission to be contacted for other research studies in the future. Consent for the optional procedures will be voluntary and will not affect regular clinical care for participants in any way.

If potential subjects are not available or not able to consent in person, they will have the option of to do a phone consent or consent through a videoconference. A HIPAA-compliant videoconferencing tool formally approved by the University of Colorado (e.g., Zoom) will be used. In order for individuals to consent remotely, subjects who want to consent by phone or video will be e-mailed or mailed a PDF of the consent form, for them to read over. They will set up a time and date with the research personnel to thoroughly go over the consent form. The prospective subject will have a written copy of the consent form in-hand at the time of the informed consent discussion, and will ask any questions she may have. For video consenting, an impartial witness must be present (site-dependent stipulation), i.e., a friend or family member of the subject or someone on the research staff who is not involved in this study. If the subject agrees to participate, the witness must sign the copy of the consent form to verify that the subject's questions were answered, and that the subject agreed to participate. The subject will send the original consent form with her signature and the witness's signature back to the Barbara Davis Center.

All subjects will fill out a questionnaire about personal demographics and baseline health history. All women will be counseled on glucose targets in pregnancy, per standard of care. Women will be given handouts on general guidelines for care of pregnant women with diabetes and on specific conditions of which they should be aware during the first trimester (see appendix). If the woman was seen at the Barbara Davis Center or Ohio State University prior to the consent visit, we will do a retrospective chart review for medications, vital signs, height/weight, A1C, insulin doses, glucose meter downloads, insulin pump downloads (if applicable), and CGM downloads (if applicable) for the most-immediate pre-conception clinic visit and for previous visits during the current pregnancy, if she was not seen at either institution prior to signing the consent form, then we will have her fill her a medical release form to request these records. Women will be asked to participate in a run-in phase. The run-in phase requires CGM wear, but not insulin pump wear. Women previously using a CGM, but not the device to be used during the run-in phase, will receive a targeted educational and training session on the study CGM system and its differences from their previous systems. Women naïve to CGM wear will receive a targeted educational and training session on CGM systems in general, on sensor wear, and on the study CGM system in particular. Both institutions in this protocol are experienced in training and starting CGM systems in pregnant women with diabetes. Women will undergo a run-in phase wherein they will wear the study CGM for 1 week and

be asked to calibrate per device instructions, log self-monitored glucose values (7 per day), insulin doses, carbohydrate intake, and exercise. Women who are compliant with device wearing and log sheets, who do not have an adverse reaction to device adhesives or wearing, who are willing to wear the study devices, and who are otherwise deemed appropriate candidates by the study PI will be invited to continue in the study (see Figure 1). The operational definition of compliance for the run-in phase is device wearing for  $\geq 80\%$  of time during the run-in phase, changing infusion sets every 3-4 days, performance of a minimum of 2 finger-sticks per day (as the HCL system requires 2-4 calibrations per day), filling out  $\geq 80\%$  of the log sheets, successful remote uploading of the CGM data, and communication with the study team during the run-in phase. Women will also be asked to record dietary (food and beverage) intake for three days during the run-in phase using log sheets. Food records will be reviewed to assess dietary compliance with the personalized pregnancy nutrition goals provided to participants and carbohydrate counting skills. Targeted enrollment after the run-in phase will be 28 women and by the end of the study will be 20 women (10 completers per group allowing for a drop-out rate of 36% due screen failures, miscarriages, dropping out, or subjects being lost to follow up).

**Figure 1: Overall Study Design**

\*2 weeks for pump-experienced participants at baseline and 4 weeks for pump-naïve participants at baseline.

\*\*Visits 7 through 14 for pregnancy care and study follow-up.

Abbreviations: CGM, continuous glucose monitor; HCL, hybrid closed-loop insulin therapy; SAPT, sensor-augmented pump therapy

Women meeting the above criteria will be trained to start SAPT mode with the Medtronic Minimed 670G insulin pump and Guardian CGM and will continue SAPT mode throughout the remainder of the 1st trimester of pregnancy. Insulin adjustments will be made every 1-7 days for the first 2 weeks. Frequency of insulin adjustments will be guided by participant experience with pump therapy, glucose levels, level of insulin sensitivity, and willingness to contact study staff to ask for assistance, where (in general) women with less pump experience, a larger-than-expected number of glucose levels above or below ADA targets, dramatic insulin sensitivity, and unwilling to proactively contact study staff for assistance will be contacted more frequently for pump follow-up and adjustments as necessary. Women will be counseled on the maternal and fetal health risks in pregnancies associated with T1D, on the ability to reduce these risks with optimal glycemic control, on

the ADA-recommended targets for glycemic control (HbA1c <6.5% prior to conception/1st trimester, HbA1c <6% as pregnancy progresses, fasting glucose target <95 mg/dL, 1-hour postprandial glucose target <140 mg/dL, and 2-hour postprandial glucose target <120 mg/dL if these can be achieved without significant hypoglycemia), and on the need for multidisciplinary care in pregnancy (diabetes expert, CDE, RD, RN, social worker, high-risk OB, eye provider, and other specialists as needed). Women with hypoglycemia unawareness will be given modified glycemic targets per ADA guidelines and the discretion of the clinical investigator. Women will be counseled on their individualized gestational weight gain goals based on guidelines from the Institute of Medicine and the American College of Gynecology, their body mass indices, lifestyle, and stage of pregnancy. They will be advised to contact the study team or study clinicians as needed to trouble shoot (e.g., for further pump adjustments, for re-training about using the 670G system, etc.) and to report AEs and SAEs throughout the duration of the study.

Women will be counseled on nutrition goals in pregnancy and will be given personalized carbohydrate goals prior to training. Table 1 provides general guidelines for appropriate gestational weight gain and changes to caloric intake based on pre-pregnancy body mass index and stage of pregnancy, however modifications will be made based on each woman’s individual situation. For example, women who are avid exercisers may have increased caloric intake goals. Guidelines are based on singleton pregnancies. Women will be given a dietary guidelines sheet describing general nutrition goals in pregnancies complicated by diabetes and their personalized goals (see appendix). Women will be asked to record all their food and beverage intake for 3 days (at least one weekday and at least one weekend day) at baseline (during the run-in phase and once each trimester). Training will include instructions for recommended infusion set changes with the appropriate time intervals and insulin reservoir fills per the relevant insulin and device labels, with set changes to be done according to the appropriate label or more frequently (if required). While in the SAPT mode, the suspend on low and suspend before low features will be disabled for the remainder of study. Women will be instructed to self-monitor blood glucose per standard of care in terms of sites allowed for sampling and frequency of checks. Women will be instructed to provide post-meal corrections as necessary, per standard of care.

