### III. Background and Significance:

Pregnancies associated with type 1 diabetes (T1D) are accompanied by high risks of adverse maternal and fetal outcomes. To reduce the risk of adverse health outcomes occurring, it is recommended that women obtain and maintain tight glycemic control throughout gestation. This task is difficult given the ever-changing insulin requirements in pregnancy. The insulin-sensitive 1st trimester predisposes women to nocturnal hypoglycemia. Insulin resistance begins 14 to 20 weeks gestation because of increased placental-fetal unit demands, free fatty acid production, and placental/maternal hormonal influences. The early post-partum period cuts insulin requirements 35-90% from pre-pregnancy doses because of cessation of placental hormones. Achieving tight glycemic targets under these conditions, without causing SH, is one of the biggest challenges of diabetes pregnancy care. For women with T1D, the high stakes and strict goals of pregnancy can negatively impact QOL and mental health. CL therapy is a novel way to improve care and QOL among pregnant women with diabetes.

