**Table 4: Conditions for Entering “Temp Target” in Auto Mode**

Condition	Justification	Duration of Use*
Exercise	Aerobic exercise causes blood glucose concentrations to fall in most people with type 1 diabetes  . While auto mode will automatically reduce micro-bolus insulin administration if sensor glucose values fall, it cannot take away active insulin from the circulation and thus may not act quickly enough to prevent hypoglycemia.	Start up to 60 minutes prior to activity, continue throughout exercise bout, stop up to 2 hours after exercise.
Impending hypoglycemia (glucose $\leq$ 70 mg/dL)	Auto mode will automatically reduce or shut off micro-bolus insulin delivery when hypoglycemia is predicted, however it cannot take away active insulin from the circulation and thus may not act quickly enough to prevent hypoglycemia. In the event that it is still delivering insulin, engaging “temp target” will reduce the amount of insulin delivered. In the event that insulin has been shut off, then engaging “temp target” for a prolonged period will allow micro-boluses to be smaller when automatic delivery resumes.	If sensor or blood glucose is 101-120 mg/dL and sensor glucose is trending down, start for 30 minutes. If sensor or blood glucose is $<$ 100 mg/dL and sensor glucose is trending down, start for 45 minutes.
Hypoglycemia (glucose $\leq$ 70 mg/dL) for more than 15 minutes	Auto mode does significantly reduce time spent in the hypoglycemic range in studies of non-pregnant populations  , but hypoglycemia may still occur. In the event that this occurs, subjects will be instructed to confirm with a blood glucose measurement, consume carbohydrates, and start a temp target. Engaging “temp target” for a prolonged period will allow micro-boluses to be smaller when automatic delivery resumes.	If blood glucose level is $<$ 50 mg/dL, start for 30 minutes. If blood glucose level is 51-69 mg/dL, start for 15 minutes.

\*Exact duration to be determined by subject’s individual responses for each condition.

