As preterm deliveries are common among pregnant women with diabetes, between 30 and 33 weeks gestation women will be given an instruction sheet detailing how to manage their insulin pumps during labor and delivery, goals for glucose management during labor and delivery, and post-partum doses and instructions (see appendix). The study staff will provide the same instructions sheets to each woman's obstetric team. We will also discuss with women their intended plan for post-study insulin delivery and glucose monitoring. Should they choose to continue therapy with a new insulin pump or glucose monitoring system, based on personal preference and health insurance coverage, we will work them to initiate paperwork for the new devices around the time of labor and delivery. They will be given instructions for transitioning to the post-study mode of insulin delivery and new glucose monitoring system (if applicable) at the final study visit. Women randomized to HCL therapy will be instructed to switch from auto mode to manual mode (until they contact the study clinician) if they are given high-dose steroids, such as betamethasone, to induce fetal lung maturation. Women in either the SAPT or HCL arms of the study will be advised to contact the study provider for instructions on pump adjustments to reduce steroid-induced hyperglycemia. The study clinician will determine when auto mode should be re-started based on the relative stability of glucose levels following steroid administration.

Women will be instructed to use manual mode for labor and delivery and until post-partum insulin sensitivity stabilizes in the immediately post-partum period. Women in the SAPT arm will remain in manual mode throughout the hospital admission if the hospital protocol allows it. Women in the HCL arm will switch to and then remain in manual mode throughout the hospital admission if the hospital protocol allows it. Women will return to clinic (or have a visit remotely by phone or Zoom) between 3 and 7 days post-partum: (1) for review of CGM, glucose meter, and pump downloads, (2) for pump adjustments to be made per the discretion of the clinical investigator, and (3) to re-initiate auto mode for women in the HCL arm per the discretion of the clinical investigator.

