The study MD or PA will examine each woman's glucose control prior to conception, during conception, and throughout pregnancy, along with A1C in the 3rd trimester, amount of gestational weight gain, and intention to breastfeed to determine the post-partum dosing. Breastfeeding often induces hypoglycemia, thus post-partum dosing will be lower for women intending to breastfeed. Because numerous clinical factors are taken into account, post-partum dosing must be individualized for each women based on the basic parameters described above and the clinical judgement of the provider. Thus, Table 4 describes basic conditions with general guidelines for post-partum pump recommendations based on changes from pre-pregnancy (or first trimester insulin pump settings, if known). If the pre-pregnancy pump settings are unknown, pump settings from term or delivery will be reduced 50-70% for the post-partum settings, with more aggressive changes in women who are intending to breastfeed. Active insulin time ranges for each individual, but typically ranges from 3-4 hours. The post-partum active insulin time recommended will be 3:15 hours  $\pm$  15 minutes (HCL group) and 3:45 hours  $\pm$  15 minutes (SAPT), per the provider's clinical judgement. We will recommend blood glucose targets over 90-120 mg/dL during the day and 100-130 mg/dL over night for the post-partum doses.

**Figure 3: Conditions with General Guidelines for Post-Partum Pump Dosing  
(Changes noted from pre-pregnancy settings, if known)**

Abbreviations: CFs, correction factors; CIs, carbohydrate-to-insulin ratios; IOM, Institute of Medicine

\*IOM guidelines for weight gain during pregnancy based on maternal body mass index

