This study's risks are minimized by use of extensive inclusion and exclusion criteria and close monitoring of research subjects. The key personnel are qualified and experienced in all of the study procedures. We will reduce the risk of severe hypoglycemia by setting a low glucose alarm of 80 mg/dL for women with hypoglycemia unawareness and 70 mg/dL for all other women, rather than relying on the mandatory 55 mg/dL low glucose alarm pre-set by the Medtronic 670G system. We will also ask each participant to keep an active glucagon kit if she already possesses one or to get an active glucagon kit if she does not have a kit or if it expired. Further, we will instruct all subjects in the HCL arm of the study that should they develop conditions that significantly reduce

insulin requirements, such as hyperemesis gravidarum, adrenal insufficiency, or placental insufficiency, that they should go into manual mode and contact the study provider for further instructions/pump adjustments. We will reduce the risk of DKA and excessive post-prandial glucose excursions by setting a high glucose alarm of 180 mg/dL for all women. We will also instruct subjects to contact the study provider if they have symptoms of DKA, elevated glucose that does not resolve with appropriate treatment, and moderate or severe ketones on testing.

The collaborators and consultants provide necessary expertise for ensuring the safety of subjects and the integrity of the study procedures. We will also use a volunteer Safety Officer to oversee the study's safety. The Safety Officer will be an independent investigator (not a member of the research team) with experience in similar clinical research. S/he will review reports of adverse events, recruitment and enrollment statistics (ethnicity and numbers of subjects disqualified, withdrawn, randomized, and who completed the study) every 6 months. This information will be reviewed during meetings with study investigators and recorded by the Safety Officer in meeting minutes.

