Potential Pitfall #2: The HCL system may not remain in auto mode continuously. The HCL system is designed to leave HCL mode under certain conditions that would affect its efficacy (e.g., prolonged loss of sensor signal). Thus, all subjects randomized to HCL therapy will also have regular adjustments made to their basal patterns and bolus wizard settings for the manual mode. Manual mode is equivalent to SAPT. Data will be collected weekly to assess frequency and etiology for leaving HCL mode. HCL exits due to subject behaviors will be addressed promptly (e.g., not wearing the sensor). A previous study done under free-living conditions wherein patients had significant alternations in glucose from exercise, medication changes, and the like showed that participants remained in HCL mode ~88% of the time. Subjects in this proposal who have HCL mode enabled  $\leq$ 80% of the time will be identified so that corrective measures can be taken (e.g., if HCL

is exited from under-calibrations then the subject will be reminded that she must calibrate 3-4 times each day).

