To address **Specific Aim 1**, we will compare percent of time spent in the SH range of <54 mg/dL on CGM (primary outcome) using a non-inferiority t-test with a margin of 1%. Counts of DKA and adverse skin reactions (secondary outcomes) will be compared between groups (HCL vs. SAPT) using t-tests for normally distributed variables and Wilcoxon Rank-Sum test for non-normal variables. As the purpose of this study is to demonstrate that HCL has a similar safety profile compared to SAPT during pregnancy, we will use a non-inferiority test. As a secondary analysis of events such as SH, DKA, and skin reactions, we will account for potential differential follow-up times due to miscarriage, drop-out, and withdrawal using Poisson regression with an offset for follow-up time. To address **Specific Aim 2**, we will compare CGM glucose variables (primary outcomes for glucose variables will be time spent <54, <63, 63-140, >140, >180 mg/dL; secondary outcomes will be glucose SD, J index, HBGI, LBG, MAGE, and CONGAn) and fear of hypoglycemia score between groups (HCL vs. SAPT) using t-tests for normally distributed variables and Wilcoxon Rank-Sum test for non-normally distributed variables. We will examine the buckets of time spent in each range (hypoglycemia, in range, and hyperglycemia) by day and night, as well as day-to-day variation. Mean glucose variables and hypoglycemia fear scores will be compared during each trimester of pregnancy and 4-6 weeks post-partum using mixed models. To address **Specific Aim 3**, we will compare SF-36 scores, insulin device satisfaction and glucose device satisfaction by group (HCL vs. SAPT) using t-tests if scores are normally distributed and Wilcoxon Rank-Sum test if scores are non-normal. We will analyze changes in INSPIRE Questionnaire scores over time in the HCL group. **Specific Aim 4** is an exploratory aim, and for this aim we will examine rates of fetal loss, preeclampsia, cesarean section, LGA, and neonatal hypoglycemia using Chi-square tests. We will account for potential differential follow-up times due to miscarriage, drop-out, and withdrawal using Poisson regression with an offset for follow-up time as a sensitivity analysis, in addition to the proposed chi-square tests in the exploratory analyses of fetal loss, preeclampsia, Caesarean section, LGA, and neonatal hypoglycemia. We will use mixed models to analyze changes in repeated measures, such as glycemia variables and hypoglycemia fear scores by trimester. We will evaluate the percent of time spent in closed loop by trimester as a feasibility outcome that is important to the next step of a larger clinical trial with efficacy outcomes.

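### Both low-glucose suspend features stay off in both arms in the first days after delivery, when the arms share manual mode and insulin need drops sharply

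*Combined protocol and SAP*

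**What the plan says.** **The setting.** The training paragraph of section C (Study Design and Research Methods) says of SAPT mode that "the suspend on low and suspend before low features will be disabled for the remainder of study". No later text re-enables either feature.

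**Whom it reaches.** Section E, Potential Pitfall #2, states: "Manual mode is equivalent to SAPT". The Introductory Background also describes the pump's manual, open mode as SAPT. The rule therefore also covers HCL women whenever they are in manual mode.

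**Mode around delivery.** The labor and delivery text of section C (after Table 4) says: "Women will be instructed to use manual mode for labor and delivery and until post-partum insulin sensitivity stabilizes in the immediately post-partum period". Both arms are to stay in manual mode through the admission if the hospital allows it. A visit 3 to 7 days post-partum reviews downloads and adjusts the pump. At that visit HCL women may restart auto mode at the clinical investigator's discretion.

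**Insulin need.** The Background and Significance section says: "The early post-partum period cuts insulin requirements 35-90% from pre-pregnancy doses because of cessation of placental hormones". The post-partum dosing paragraph of section C adds that breastfeeding often brings on hypoglycemia.

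**Protections.** Post-partum doses are individualized (Figure 3 and its text). Glucose targets are raised to 90-120 mg/dL by day and 100-130 mg/dL at night. Low alarms are set at 70 mg/dL, or 80 mg/dL for hypoglycemia unawareness, and women are asked to keep a glucagon kit. The woman and her obstetric team receive written delivery and post-partum instructions between 30 and 33 weeks.

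**The concern.** Keeping the comparator free of automated insulin suspension is a sensible reason for the setting while one arm is in auto mode and the other is not. From delivery until auto mode restarts, neither arm is in auto mode, so that reason is absent. The protocol itself describes these days as a time of steep and variable falls in insulin need, yet the one pump function that would stop insulin at a low sensor reading is off for every woman still wearing the pump.

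What is at stake is mainly participant safety in a short window. There is also a consequence for the study. Severe hypoglycemia and time below 54 mg/dL are assessed through early post-partum. Table 5 counts severe events from any cause toward the individual limit of three, and events in the whole cohort toward the study limit of seven. Events in days with no contrast in delivery mode would count toward those limits.

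**Working it through.** The plan gives no figure on this point, so there is none to reproduce. The check sets the provisions side by side and then sizes the window.

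**1. Is there a contrast in delivery mode?**

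| Period | HCL arm | SAPT arm | Suspend features in manual mode |
|---|---|---|---|
| Randomization to labor | Auto mode, with exits to manual | Manual | Off |
| Delivery to the 3-7 day visit | Manual | Manual | Off |
| After the visit | Auto, when the investigator restarts it | Manual | Off |

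In the middle row the mode and the suspend setting are identical in both arms. Switching a feature on in both arms leaves them identical.

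**2. How wide is the range of need?** A fall of 35% leaves 1 - 0.35 = 0.65 of the pre-pregnancy dose, and a fall of 90% leaves 1 - 0.90 = 0.10. Need in this period is thus 10-65% of the pre-pregnancy dose. This describes variation in need. It is not an error in the planned doses.

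**3. How many days?** Counting from delivery to the visit gives 3 to 7 days per woman, fewer if the hospital removes the pump.
- For the 20 planned completers: 20 × 3 = 60 to 20 × 7 = 140 woman-days, half of them in each arm.
- Share of the 6-week (42-day) post-partum follow-up: 3/42 = 7.1% to 7/42 = 16.7%.
- Share of post-randomization time: days = (delivery week - randomization week) × 7 + 42. Randomization at 12-14 weeks and delivery at 34-40 weeks are assumed.
  - Longest follow-up: (40 - 12) × 7 + 42 = 238 days; 3/238 = 1.3%.
  - Shortest follow-up: (34 - 14) × 7 + 42 = 182 days; 7/182 = 3.8%.

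The window is therefore about 1-4% of post-randomization time. Auto mode restarts at discretion, so an HCL woman's manual period under the current rule can run beyond day 7.

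**4. Which analyses see these days?** Section F says the mean glucose variables and fear scores "will be compared during each trimester of pregnancy and 4-6 weeks post-partum using mixed models". That post-partum time point lies after the window. The Aim 1 non-inferiority test of time below 54 mg/dL has no such limit, and Aim 1 covers early post-partum, so these days may enter it.

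Suppose each woman's percentage is an average over all post-randomization days with even sensor wear (an assumption). Then each percentage point of between-arm difference removed from the window moves the whole-period difference by 3/238 = 0.013 to 7/182 = 0.038 points. The margin is 1% in the analysis text and 1.5% in the power text.

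**The case against.** **The arms share a mode but not a history.** SAPT women have lived on their manual settings throughout, while HCL women return to settings kept in the background. How safely they return is arguably part of the HCL strategy, and the Background section names the shift to post-partum insulin sensitivity as a point of interest. But that interest concerns how the PID algorithm copes, and the algorithm is off in these days. Both arms also start from provider-set post-partum doses. What stands is that a difference in these days could count in Aim 1, and a suspend feature in both arms could shrink it. In a non-inferiority test that leans toward passing, though by very little (step 4). It would be too much to say that the change costs the comparison nothing.

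**Protection is already in place.** Part of the window is a hospital stay with staff who hold the instruction sheet, so safety does not rest on the woman alone. This is fair, and it lowers the risk. But the listed measures work through a dose chosen in advance or through someone acting on an alarm.

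**Some material cannot be seen.** Figure 3 and the instruction sheet are not in the text reviewed and may say more. The protocol sentence as written still allows no exception.

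**Suspension is imperfect.** A falsely low reading could interrupt basal insulin. Acetaminophen falsely raises sensor glucose (section D), so suspension could fail to trigger. Both points stand. The 180 mg/dL high alarm and ketone instructions cover the first, and the second limits the benefit.

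**Stronger readings that a reader might infer.**
- *The same change is needed in pregnancy.* HCL women with conditions that lower "insulin requirements, such as hyperemesis gravidarum, adrenal insufficiency, or placental insufficiency, that they should go into manual mode" do leave a mode that can reduce or stop delivery. But only the affected woman changes mode, the randomized comparison is still running, and switching suspend on for SAPT women in that situation would alter the comparator.
- *Women would receive several times the insulin they need.* The text "pump settings from term or delivery will be reduced 50-70% for the post-partum settings" is a fallback for unknown pre-pregnancy settings. Dosing is individualized, with larger cuts for women who intend to breastfeed, so multiples computed from the extremes are not doses in the plan.

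**Conclusion.** The point holds for the period from delivery until auto mode is restarted at or after the 3-7 day visit. In those days the disabled features preserve no difference in delivery mode, and the protocol itself describes sharply reduced insulin need and a tendency to hypoglycemia. The existing safeguards are real but do not stop insulin automatically. This is a cheap improvement to consider. It does not threaten the trial's validity.

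The size is 3 to 7 days per woman, about 1-4% of post-randomization time. No effect on time below 54 mg/dL or on severe hypoglycemia is claimed, because the documents give no basis for one.

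The conclusion rests on manual mode counting as SAPT mode for HCL women, on the pump staying on after delivery, and, for the percentages, on the assumed randomization and delivery weeks. It does not extend to the lead-in or to the rest of pregnancy, where keeping the features off in manual mode is not disputed.

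**What to change.** 1. In section C, amend the SAPT training paragraph and the labor and delivery text: from delivery to the 3-7 day visit, suspend on low is switched on in both arms wherever the study pump is worn.
2. At that visit, switch it off again in both arms. This covers SAPT women and any HCL woman who is still in manual mode, so that the arms remain alike within manual mode even when the auto-mode restart is delayed.
3. Add the instruction to the delivery sheet given between 30 and 33 weeks to the woman and her obstetric team.
4. Record the on and off dates from the pump downloads already collected.

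**Cost.** Two amended sentences, one line on an existing handout and two dates per woman. No sample-size input changes, and the 4-6 week post-partum comparison is untouched. About 1-4% of post-randomization days would fall under the new setting, equally in both arms, with the possible slight dilution of the Aim 1 difference shown above. The clinical downside is interruption of basal insulin after a falsely low reading, for which the high alarm and ketone instructions already provide.
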